129.	Table 15.3.4.1.1	Physical Examination – Safety Set	T15_03_04_01_01_pe_ss
130.	Table 15.3.5.1.1	Gynecological Examination – Safety Set	T15_03_05_01_01_gyn_exam_ss
131.	Table 15.3.6.1.1	Transvaginal Ultrasound Examination – Safety Set	T15_03_06_01_01_transvag_exam_ss
132.	Table 15.3.6.1.2	Shift Table for Transvaginal Ultrasound Examination – Safety Set	T15_03_06_01_02_transvag_exam_shift_ss
133.	Table 15.3.7.1.1	Dysmenorrhea Characteristic – Safety Set	T15_03_07_01_01_dysm_char_ss
134.	Table 15.3.7.1.2	Shift Table for Dysmenorrhea – Safety Set	T15_03_07_01_02_dysm_char_shift_ss
135.	Table 15.3.8.1.1	Mastodynia/Mastalgia Characteristic – Safety Set	T15_03_08_01_01_mastodyn_char_ss
136.	Table 15.3.8.1.2	Shift Table for Mastodynia/Mastalgia – Safety Set	T15_03_08_01_02_mastodyn_char_shift_ss
137.	Table 15.3.9.1.1	Summary of Cervical Cytology – Safety Set	T15_03_09_01_01_cytology_ss
138.	Table 15.3.9.1.2	Shift Table for Cervical Cytology Test – Safety Set	T15_03_09_01_02_cytology_shift_ss
Tolerability Data			
139.	Table 15.4.1.1.1	Number of Subjects with Bleeding by Treatment Day, Treatment Cycle and Reference Period – Full Analysis Set	T15_04_01_01_01_sub_bleed_day_cyc_ref_fas
140.	Table 15.4.1.2.1	Number of Subjects with Unscheduled Bleeding Days by Treatment Cycle and Reference Period – Full Analysis Set	T15_04_01_02_01_sub_uebleed_cyc_ref_fas
141.	Table 15.4.1.3.1	Number of Subjects with Scheduled Bleeding Days by Treatment Cycle and Reference Period – Full Analysis Set	T15_04_01_03_01_sub_sbleed_cyc_ref_fas
142.	Table 15.4.1.4.1	Number of Days with Bleeding by Cycle and Reference Period – Full Analysis Set	T15_04_01_04_01_day_bleed_cyc_ref_fas
143.	Table 15.4.1.5.1	Number of Days with Unscheduled Bleeding by Cycle and Reference Period – Full Analysis Set	T15_04_01_05_01_day_uebleed_cyc_ref_fas
144.	Table 15.4.1.6.1	Number of Days with Scheduled Bleeding by Cycle and Reference Period – Full Analysis Set	T15_04_01_06_01_day_sbleed_cyc_ref_fas
145.	Table 15.4.2.1.1	Number of Subjects with Spotting by Treatment Day, Treatment Cycle and Reference Period – Full Analysis Set	T15_04_02_01_01_sub_spot_day_cyc_ref_fas

146.	Table 15.4.2.2.1	Number of Subjects with Unscheduled Spotting Days by Treatment Cycle and Reference Period – Full Analysis Set	T15_04_02_02_01_sub_uspot_cyc_ref_fas
147.	Table 15.4.2.3.1	Number of Subjects with Scheduled Spotting Days by Treatment Cycle and Reference Period – Full Analysis Set	T15_04_02_03_01_sub_sspot_cyc_ref_fas
148.	Table 15.4.2.4.1	Number of Days with Spotting by Cycle and Reference Period – Full Analysis Set	T15_04_02_04_01_day_spot_cyc_ref_fas
149.	Table 15.4.2.5.1	Number of Days with Unscheduled Spotting by Cycle and Reference Period – Full Analysis Set	T15_04_02_05_01_day_uspot_cyc_ref_fas
150.	Table 15.4.2.6.1	Number of Days with Scheduled Spotting by Cycle and Reference Period – Full Analysis Set	T15_04_02_06_01_day_sspot_cyc_ref_fas
151.	Table 15.4.3.1.1	Number of Bleeding/Spotting Episodes During Treatment and by Reference Period – Full Analysis Set	T15_04_03_01_01_epis_trt_ref_fas
152.	Table 15.4.3.2.1	Duration of Bleeding/Spotting Episodes by Cycle and Reference Period – Full Analysis Set	T15_04_03_02_01_epis_dur_cyc_ref_fas
153.	Table 15.4.3.3.1	Number of Subjects with Prolonged Bleeding/Spotting >9 and >14 by Reference Period – Full Analysis Set	T15_04_03_03_01_sub_pblsp_9_14_ref_fas
154.	Table 15.4.4.1.1_add	Number of Subjects with Bleeding/Spotting by Treatment Day, Treatment Cycle and Reference Period – Full Analysis Set	T15_04_04_01_01_sub_bfsp_fas
155.	Table 15.4.4.2.1_add	Number of Subjects with Unscheduled Bleeding/Spotting Days by Treatment Cycle and Reference Period – Full Analysis Set	T15_04_04_02_01_sub_ubfsp_fas
156.	Table 15.4.4.3.1_add	Number of Subjects with Scheduled Bleeding/Spotting Days by Treatment Cycle and Reference Period – Full Analysis Set	T15_04_04_03_01_sub_sbfsp_fas
157.	Table 15.4.5.1.1_add	Number of Subjects with no Bleeding/Spotting Days by Treatment Cycle and Reference Period – Full Analysis Set	T15_04_05_01_01_sub_no_bfsp_fas
158.	Table 15.4.6.1.1_add	Number of Days with Bleeding/Spotting by Cycle and Reference Period in BMI Subgroup – Full Analysis Set	T15_04_06_01_01_days_bfsp_BMI_fas
159.	Table 15.4.6.2.1_add	Number of Days with Unscheduled Bleeding/Spotting by Cycle and Reference Period in BMI Subgroup – Full Analysis Set	T15_04_06_02_01_days_ubfsp_BMI_fas
160.	Table 15.4.6.3.1_add	Number of Days with Scheduled Bleeding/Spotting by Cycle and Reference Period in BMI Subgroup – Full Analysis Set	T15_04_06_03_01_days_sbfsp_BMI_fas
161.	Table 15.4.7.1.1_add	Number of Days with Bleeding/Spotting by Cycle and Reference Period in Weight Subgroup – Full Analysis Set	T15_04_07_01_01_days_bfsp_weight_fas
162.	Table 15.4.7.2.1_add	Number of Days with Unscheduled Bleeding/Spotting by Cycle and Reference Period in Weight Subgroup – Full Analysis Set	T15_04_07_02_01_days_ubfsp_weight_fas
163.	Table 15.4.7.3.1_add	Number of Days with Scheduled Bleeding/Spotting by Cycle and Reference Period in Weight Subgroup – Full Analysis Set	T15_04_07_03_01_days_sbfsp_weight_fas
164.	Table 15.4.7.1.1	IMP Acceptability Assessment – Full Analysis Set	T15_04_07_01_01_imp_accept_fas
165.	Table 15.4.7.2.1	Shift table for IMP Acceptability Assessment – Full Analysis Set	T15_04_07_02_01_shift_imp_accept_fas

5. Listings

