5.7.1 Bleeding Pattern

The number and rate of subjects with different bleeding and spotting patterns will be presented for each cycle. The Clopper-Pearson 95% CI for vaginal bleeding or spotting rate of subjects will be calculated using the **PROC FREQ** procedure:

```
PROC FREQ DATA=<data set>;
  BY <by variable>;
  TABLES <endpoint variable> / BINOMIAL;
RUN;
```

The following definitions will be applied:

Episode of bleeding/spotting – bleeding/spotting days bounded on either end by two days of no bleeding or spotting. Missing data will be considered as bleeding/spotting day if it is bounded on bleeding/spotting days or one days of no bleeding or spotting.

Days of bleeding/spotting – presence of bleeding/spotting on actual day.

Scheduled bleeding/spotting – any bleeding or spotting that occurs during hormone-free intervals (defined as Days 25-28 ± 1 day). Bleeding/spotting that starts during this period and continues for up to eight consecutive days is considered as scheduled bleeding/spotting.

If scheduled bleeding starts in Cycle X but ends in Cycle (X+1) then bleeding episode will be assigned to Cycle X.

Any bleeding or spotting that occurs during cycle Days [1-8] of the first treatment cycle and lasts up to 8 consecutive bleeding/spotting days will also be considered as scheduled bleeding days.

Unscheduled bleeding/spotting – any bleeding/spotting that occurs outside the time window defined for scheduled bleedings.

Cumulative rate of subjects with different bleeding and spotting patterns for reference periods (summary of cycles 2-4, 5-7, 8-10 and 11-13) will be provided. Cumulative rates only for reference periods will also be presented for number and percent of subjects with prolonged bleeding and spotting > 9 days/ > 14 days and the number of bleeding and spotting episodes.

Number and percent of days per cycle and reference period with bleeding and spotting, scheduled bleeding, unscheduled bleeding, scheduled spotting or unscheduled spotting and duration of scheduled bleeding, scheduled spotting, unscheduled bleeding and unscheduled spotting will be analyzed descriptively.

Cycles without consecutively missing diary entries and with less than five non-consecutive missing diary entries will be used in the bleeding pattern analysis.

Tables

No.	Name	Analysis set	Comments

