Table 15.4.1.1.1	Number of Subjects with Bleeding by Treatment Day, Treatment Cycle and Reference Period	Full Analysis	Number and percentage of subjects in respective time point will be presented. Percentage will be based on the number of subjects with respective cycles available. Data of centers 104 and 120 will be excluded.
Table 15.4.1.2.1	Number of Subjects with Unscheduled Bleeding Days by Treatment Cycle and Reference Period	Full Analysis	Number and percentage of subjects in respective time point will be presented. Percentage will be based on the number of subjects with respective cycles available. Data of centers 104 and 120 will be excluded.
Table 15.4.1.3.1	Number of Subjects with Scheduled Bleeding Days by Treatment Cycle and Reference Period	Full Analysis	Number and percentage of subjects in respective time point will be presented. Percentage will be based on the number of subjects with respective cycles available. Data of centers 104 and 120 will be excluded.
Table 15.4.1.4.1	Number of Days with Bleeding by Cycle and Reference Period	Full Analysis	Number of days will be summarized as continuous data. Number of days will be based on the number of subjects with respective cycles available. Data of centers 104 and 120 will be excluded.
Table 15.4.1.5.1	Number of Days with Unscheduled Bleeding by Cycle and Reference Period	Full Analysis	Number of days will be summarized as continuous data. Number of days will be based on the number of subjects with respective cycles available. Data of centers 104 and 120 will be excluded.
Table 15.4.1.6.1	Number of Days with Scheduled Bleeding by Cycle and Reference Period	Full Analysis	Number of days will be summarized as continuous data. Number of days will be based on the number of subjects with respective cycles available. Data of centers 104 and 120 will be excluded.
Table 15.4.2.1.1	Number of Subjects with Spotting by Treatment Day, Treatment Cycle and Reference Period	Full Analysis	Number and percentage of subjects in respective time point will be presented. Percentage is based on subject with respective cycle available. Data of centers 104 and 120 will be excluded.
Table 15.4.2.2.1	Number of Subjects with Unscheduled Spotting Days by Treatment Cycle and Reference Period	Full Analysis	Number and percentage of subjects in respective time point will be presented. Percentage will be based on the number of subjects with respective cycles available. Data of centers 104 and 120 will be excluded.

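### By-treatment-day bleeding percentages keep women without a diary entry that day in the denominator, and the SAP does not say how missing days enter the day counts

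*SAP*

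**What the plan says.** All references are to the SAP.

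- **Which cycles are analysed (5.7.1):** "Cycles without consecutively missing diary entries and with less than five non-consecutive missing diary entries will be used in the bleeding pattern analysis". At most four days of a retained cycle can be missing.
- **Episode (5.7.1):** "bleeding/spotting days bounded on either end by two days of no bleeding or spotting". The same entry adds: "Missing data will be considered as bleeding/spotting day if it is bounded on bleeding/spotting days or one days of no bleeding or spotting".
- **Day of bleeding/spotting (5.7.1):** "presence of bleeding/spotting on actual day". Nothing is said about a day without an entry.
- **By-treatment-day tables:** these are 15.4.1.1.1 (titled "Number of Subjects with Bleeding by Treatment Day, Treatment Cycle and Reference Period – Full Analysis Set"), 15.4.2.1.1 for spotting and 15.4.4.1.1_add for the two combined. The comment for the first and third reads "Percentage will be based on the number of subjects with respective cycles available"; the spotting table has the same rule in slightly different words.
- **Day-count tables:** "Number of days will be based on the number of subjects with respective cycles available". No adjustment for missing days is stated.
- **Elsewhere:** Section 4.1 sets a default of percentages over subjects with non-missing data. Section 4.10 refers missing-data handling to the subsections of Section 5. Section 2.2.4 restricts the bleeding analysis to cycles with complete and correct diary entries, and Section 4.8 defines a complete record as one with date, bleeding status and amount all present.

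**The concern.** The retention rule lets missing days into the analysis, and the by-day denominator then ignores that they are missing. A woman without an entry on a given day stays in the denominator and cannot enter the numerator.

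The second difficulty is a gap. The one rule that fills missing days is written for episodes, and the SAP does not say whether it also governs the counts of bleeding days. If it does not, two tables built from the same diary can describe the same woman differently.

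Vaginal bleeding pattern makes up most of the tolerability endpoints. The trial has one arm, so there is no comparison in which a shared error could cancel; the absolute rates are the result. The primary Pearl Index is not affected.

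**Working it through.** **Inputs.** Cycle length is 28 days (Section 4.6). A retained cycle has at most 4 missing days, none adjacent (5.7.1). Denominators come from the table comments. The documents give no frequency of missing entries, so 3% to 10% of days is used as an assumption.

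**1. By-day rate.** Let N women have the cycle available, let a share m have no entry on the day, and let r be the true proportion bleeding. If missingness is unrelated to bleeding and the day is not filled:

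- planned: N(1 − m)r / N = (1 − m)r, a relative understatement of m;
- with women who have an entry as denominator: N(1 − m)r / [N(1 − m)] = r.

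**2. Ceiling.** With 1, 2 or 4 missing days per cycle, m averages 1/28 = 3.6%, 2/28 = 7.1% or 4/28 = 14.3% over the cycle. The ceiling is the same for a three-cycle reference period (12/84) and for cycles 2-13 (48/336). A single day can lie above the average.

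**3. Size under the assumed range.** If each day is missing independently with probability p, a retained cycle with k missing days has weight C(29 − k, k) p^k (1 − p)^(28 − k), for k = 0 to 4.

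| p | Mean missing days, retained cycles | Divided by 28 |
|---|---|---|
| 3% | 0.79 | 2.8% |
| 5% | 1.26 | 4.5% |
| 8% | 1.85 | 6.6% |
| 10% | 2.17 | 7.7% |

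**4. Does the episode rule cure this?** Only in part. It acts only where neighbouring days meet its condition. In a simulation (20,000 cycles per setting; one run of 3, 5, 8 or 12 bleeding days; 1, 2 or 4 non-consecutive missing days placed at random) it filled 4% to 36% of missing days if both neighbours must be bleeding days (strict reading). It filled 17% to 49% if one is enough (loose reading). The reference to one day of no bleeding leaves open which reading is meant. A filled day is also of no stated type, so it cannot be placed in the separate bleeding and spotting tables.

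**5. Episodes against day counts.** B is a bleeding/spotting day and M a missing day; all other days are bleed-free. Each cycle would be retained.

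| Diary | Recorded days | Episode length |
|---|---|---|
| B M B M B | 3 | 5 |
| B B M B B | 4 | 5 |
| B M B M B M B M B B | 6 | 10 |
| B M | 1 | 1 (strict) or 2 (loose) |
| M alone | 0 | 0 |

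The third woman exceeds the 9-day threshold for prolonged bleeding/spotting in Table 15.4.3.3.1 while direct counting gives her six days. The last row shows no disagreement.

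**6. Direction of error in the day counts.** In the same simulation, recorded days were about 0.96, 0.93 and 0.86 of true days with 1, 2 and 4 missing days and no filling. With the rule carried over to combined counts, the ratio was 0.907 to 0.994 (strict) or 1.005 to 1.092 (loose). So the sign depends on a reading that the SAP leaves open.

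**The case against.** Four points can be made for the plan.

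- **Section 4.1 already uses non-missing data.** Under that default a woman without an entry would drop out for that day, and the wording in the table comments is shared by by-day, by-cycle and by-period results, so it may be boilerplate. But a table-specific comment takes precedence over a general default. At best the two conflict, and the conflict needs settling.
- **The filling rule may apply throughout 5.7.1.** It stands among the general definitions, directly before that of a bleeding/spotting day. On that reading the combined day counts agree with the episodes. This is a fair reading, and it means the disagreement in the examples is conditional. It does not repair the by-day denominator, because most missing days are not filled and filled days have no type.
- **Sections 2.2.4 and 4.8 ask for complete entries.** If they governed, the question would not arise. They conflict with the explicit retention rule in 5.7.1. The data review meeting is asked to define a complete and correct entry (Section 3.3), but that would not by itself say how a missing day inside a retained cycle is counted.
- **The rate may be small.** This is true; the documents give none, and 14.3% is a ceiling.

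A reader might go further and infer that every missing day is treated as bleed-free in the day tables and as bleeding in the episode tables, and that bleeding is therefore understated throughout. The documents do not support this. No section states a bleed-free rule for day counts, the episode rule is conditional, and under the loose reading combined counts would be overstated.

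**Conclusion.** The by-day point holds as the SAP is written: all three by-treatment-day tables understate the rate by about the share of entries missing on that day. That is at most 14.3% in relative terms on average over a cycle, and about 3% to 8% if 3% to 10% of days are missing at random. These figures assume that missingness is unrelated to bleeding and that the day is not filled; filling reduces the understatement only in part, and only where the combined category is reported.

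For the day-count tables the finding is narrower. The SAP does not state the rule, and if the episode rule is not carried over, episode and day-count tables can disagree for the same diary. Neither a general understatement of day counts nor a contradiction in every case follows from the text.

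**What to change.** 1. **By-day denominator.** In Tables 15.4.1.1.1, 15.4.2.1.1 and 15.4.4.1.1_add, base the by-treatment-day percentages on women with a diary entry on that day.
2. **One stated missing-day rule for all day-count tables.** Include the BMI and weight tables (Nos. 158-163 in the table list). Use either the episode rule, which can serve only the combined bleeding/spotting tables, or scaling as recorded days × 28 / days with an entry. Do not use both in one table. Say whether one or both neighbours must be bleeding days. Scaling corrects the average but does not match a woman's episode length: in the first example it gives 3 × 28/26 = 3.2 days against a 5-day episode. If it is chosen, a footnote should say so.
3. **Reconcile** the complete-entries wording of Sections 2.2.4 and 4.8 with the retention rule in 5.7.1.

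Incomplete cycles with no recorded bleeding should not be removed selectively from the table titled "Number of Subjects with no Bleeding/Spotting Days by Treatment Cycle and Reference Period – Full Analysis Set" (15.4.5.1.1_add). At 3% missing, only 0.97^28 / 0.976 = 43.7% of retained cycles are complete. If 40% of cycles were truly bleed-free (assumption), selective removal would report about 0.4 × 0.437 / (0.4 × 0.437 + 0.6) = 22.5%, a larger distortion than the one being corrected. At most, add a sensitivity table restricted to all cycles with no missing day, whatever their bleeding status.

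The cost is SAP wording and minor programming. Reported by-day rates will be slightly higher.

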Appendix tables defined below will be provided in separate .rtf files for each output.

Seq. No	Table No and Title		Output file name
Demographic and Study Population Data			
1.	Listing 16.2.1.1	Reasons for Exclusion from Analysis Sets – Enrolled Set	L16_02_01_01_excl_es
2.	Listing 16.2.1.2	Subject's Disposition – Safety Set	L16_02_01_02_disp_ss

3.	Listing 16.2.1.3	Subject Visits – Enrolled Set	L16_02_01_03_visits_es
4.	Listing 16.2.1.4	Protocol Deviations Reported by Investigator – Enrolled Set	L16_02_01_04_dev_inv_es
5.	Listing 16.2.1.5	Screening Failures – Enrolled Set	L16_02_01_05_scren_fail_es
6.	Listing 16.2.1.6	Inclusion Criteria Not Met and Exclusion Criteria Met	L16_02_01_06_incl_excl_es
7.	Listing 16.2.1.7	Demographics – Enrolled Set	L16_02_01_07_demo_es
8.	Listing 16.2.1.8	Substance Use – Enrolled Set	L16_02_01_08_subst_use_es
9.	Listing 16.2.1.9	Medical History – Enrolled Set	L16_02_01_09_mh_es
10.	Listing 16.2.1.10	Gynecological History – Enrolled Set	L16_02_01_10_gyn_his_es
11.	Listing 16.2.1.11	VTE Risk Factors – Enrolled Set	L16_02_01_11_vte_es
12.	Listing 16.2.1.12	Menstrual History – Enrolled Set	L16_02_01_12_menstr_his_es
13.	Listing 16.2.1.13	Prior and Concomitant Medications, Therapies and Contraception – Enrolled Set	L16_02_01_13_cm_es
14.	Listing 16.2.1.14	Drug Accountability – Enrolled Set	L16_02_01_14_drug_account_es
15.	Listing 16.2.1.15	Treatment Compliance According to Drug Accountability – Enrolled Set	L16_02_01_15_compl_es
Efficacy Data			
16.	Listing 16.2.2.1	Pregnancy Determination – Enrolled Set	L16_02_02_01_preg_determ_es
17.	Listing 16.2.2.2	Pregnancy Outcome – Enrolled Set	L16_02_02_02_preg_out_es
18.	Listing 16.2.2.3	Subjects' Decision to Become Pregnant – Enrolled Set	L16_02_02_03_decis_preg_es
Safety Data			
19.	Listing 16.2.3.1	Adverse Event: General – Enrolled Set	L16_02_03_01_ae_es
20.	Listing 16.2.3.2	Adverse Event: MedDRA Coding – Enrolled Set	L16_02_03_02_ae_meddra_es
21.	Listing 16.2.3.3	Serious Adverse Event – Enrolled Set	L16_02_03_03_sae_es
22.	Listing 16.2.3.4	TEAEs Leading to Trial Termination - Enrolled Set	L16_02_03_04_tae_term_es
23.	Listing 16.2.3.5	TEAEs of Special Interest – Enrolled Set	L16_02_03_05_tae_sp_int_es
24.	Listing 16.2.4.1	Vital Signs – Enrolled Set	L16_02_04_01_vs_es
25.	Listing 16.2.5.1	Laboratory Data: Hematology – Enrolled Set	L16_02_05_01_hema_es
26.	Listing 16.2.5.2	Laboratory Data: Biochemistry – Enrolled Set	L16_02_05_02_bioch_es
27.	Listing 16.2.5.3	Laboratory Data: Urinalysis – Enrolled Set	L16_02_05_03_urin_es
28.	Listing 16.2.5.4	Laboratory Data: Pregnancy Test – Enrolled Set	L16_02_05_04_preg_es
29.	Listing 16.2.6.1	Physical Examination – Enrolled Set	L16_02_06_01_pe_es
30.	Listing 16.2.7.1	Gynecological Examination – Enrolled Set	L16_02_07_01_gyn_exam_es
31.	Listing 16.2.7.2	Transvaginal Ultrasound Examination – Enrolled Set	L16_02_07_02_transv_exam_es
32.	Listing 16.2.7.3	Dysmenorrhea Characteristic – Enrolled Set	L16_02_07_03_dysm_char_es
33.	Listing 16.2.7.4	Mastodynia/Mastalgia – Enrolled Set	L16_02_07_04_mastod_char_es
34.	Listing 16.2.8.1	Cervical Cytology Results – Enrolled Set	L16_02_08_01_cytol_es
Tolerability Data			
35.	Listing 16.2.9.1	Treatment Diary – Full Analysis Set	L16_02_09_01_diary_fas
36.	Listing 16.2.10.1	IMP Acceptability Assessment – Full Analysis Set	L16_02_10_01_imp_accept_fas

6. Figures

Appendix figures defined below will be provided in separate .rtf files for each output.

Seq. No	Table No and Title		Output file name
Demographic and Study Population Data			
1.	Figure 15.1.1.1	Flow Chart of Subject Disposition – Enrolled Set	F15_01_01_01_disp_es
2.	Figure 15.1.2.1	Flow Chart of Analysis Sets – Enrolled Set	F15_01_02_01_anal_es
Tolerability Data			
3.	15.2.1.1_add	Overall Pearl Index in Non-Breastfeeding Women by BMI and Race (Black or African-American vs White) (Only Confirmed Pregnancies, Excluding Sites 104 and 120) – Modified Full Analysis Set	F15_02_01_01_PI_over_BMI_C_E_race_mfas

4.	Figure 15.2.1.2_add Overall Pearl Index in Non-Breastfeeding Women by BMI and Race (Black or African-American vs White) (Only Confirmed Pregnancies, Including Sites 104 and 120) – Modified Full Analysis Set	F15_02_01_02_PI_over_BMI_C_I_race_mfas
5.	Figure 15.2.1.3_add Overall Pearl Index in Non-Breastfeeding Women by BMI and Race (Black or African-American vs White) (Confirmed and Suspected, Non-confirmed Pregnancies, Excluding Sites 104 and 120) – Modified Full Analysis Set	F15_02_01_03_PI_over_BMI_CS_E_race_mfas
6.	Figure 15.2.1.4_add Overall Pearl Index in Non-Breastfeeding Women by BMI and Race (Black or African-American vs White) (Confirmed and Suspected, Non-confirmed Pregnancies, Including Sites 104 and 120) – Modified Full Analysis Set	F15_02_01_04_PI_over_BMI_CS_I_race_mfas
7.	Figure 15.2.2.1_add Overall Pearl Index in Non-Breastfeeding Women by BMI and Ethnicity (Only Confirmed Pregnancies, Excluding Sites 104 and 120) – Modified Full Analysis Set	F15_02_02_01_PI_over_BMI_C_E_ethnicity_mfas
8.	Figure 15.2.2.2_add Overall Pearl Index in Non-Breastfeeding Women by BMI and Ethnicity (Only Confirmed Pregnancies, Including Sites 104 and 120) – Modified Full Analysis Set	F15_02_02_02_PI_over_BMI_C_I_ethnicity_mfas
9.	Figure 15.2.2.3_add Overall Pearl Index in Non-Breastfeeding Women by BMI and Ethnicity (Confirmed and Suspected, Non-Confirmed Pregnancies, Excluding Sites 104 and 120) – Modified Full Analysis Set	F15_02_02_03_PI_over_BMI_CS_E_ethnicity_mfas
10.	Figure 15.2.2.4_add Overall Pearl Index in Non-Breastfeeding Women by BMI and Ethnicity (Confirmed and Suspected, Non-confirmed Pregnancies, Including Sites 104 and 120) – Modified Full Analysis Set	F15_02_02_04_PI_over_BMI_CS_I_ethnicity_mfas
11.	Figure 15.2.3.1_add Pearl Index Based on Evaluable Cycles in Non-Breastfeeding Women by BMI and Race (Black or African-American vs White) (Only Confirmed Pregnancies, Excluding Sites 104 and 120) – Modified Full Analysis Set	F15_02_03_01_PI_eval_BMI_C_E_race_mfas
12.	Figure 15.4.1.1 Subjects with Bleeding by Treatment Day – Full Analysis Set	F15_04_01_01_sub_bleed_day_fas
13.	Figure 15.4.1.2 Subjects with Bleeding by Treatment Cycle – Full Analysis Set	F15_04_01_02_sub_bleed_cyc_fas
14.	Figure 15.4.1.3 Subjects with Bleeding by Reference Period – Full Analysis Set	F15_04_01_03_sub_bleed_ref_fas
15.	Figure 15.4.2.1 Subjects with Scheduled and Unscheduled Bleeding Days by Treatment Cycle – Full Analysis Set	F15_04_02_01_sub_subleed_cyc_fas
16.	Figure 15.4.2.2 Subjects with Scheduled and Unscheduled Bleeding Days by Reference Period – Full Analysis Set	F15_04_02_02_sub_subleed_ref_fas
17.	Figure 15.4.4.1 Scheduled and Unscheduled Bleeding Days by Cycle – Full Analysis Set	F15_04_04_01_subleed_day_cyc_fas
18.	Figure 15.4.4.2 Scheduled and Unscheduled Bleeding Days by Reference Period – Full Analysis Set	F15_04_04_02_subleed_day_ref_fas
19.	Figure 15.4.5.1 Subjects with Spotting by Treatment Day – Full Analysis Set	F15_04_05_01_sub_spot_day_fas
20.	Figure 15.4.5.2 Subjects with Spotting by Treatment Cycle – Full Analysis Set	F15_04_05_02_sub_spot_cyc_fas
21.	Figure 15.4.5.3 Subjects with Spotting by Reference Period – Full Analysis Set	F15_04_05_03_sub_spot_ref_fas
22.	Figure 15.4.6.1 Subjects with Scheduled and Unscheduled Spotting Days by Treatment Cycle – Full Analysis Set	F15_04_06_01_sub_suspot_cyc_fas
23.	Figure 15.4.6.2 Subjects with Scheduled and Unscheduled Spotting Days by Reference Period – Full Analysis Set	F15_04_06_02_sub_suspot_ref_fas
24.	Figure 15.4.7.1 Bleeding/Spotting Episodes by Reference Period – Full Analysis Set	F15_04_07_01_epis_ref_fas

25.	Figure 15.4.8.1	Scheduled and Unscheduled Spotting Days by Cycle – Full Analysis Set	F15_04_08_01_suspot_day_cyc_fas
26.	Figure 15.4.8.2	Scheduled and Unscheduled Spotting Days by Reference Period – Full Analysis Set	F15_04_08_02_suspot_day_ref_fas
27.	Figure 15.4.9.1_add	Subjects with Bleeding/Spotting by Treatment Day – Full Analysis Set	F15_04_09_01_sub_bfsp_day_fas
28.	Figure 15.4.9.2_add	Subjects with Bleeding/Spotting by Treatment Cycle – Full Analysis Set	F15_04_09_02_sub_bfsp_cyc_fas
29.	Figure 15.4.9.3_add	Subjects with Bleeding/Spotting by Reference Period – Full Analysis Set	F15_04_09_03_sub_bfsp_ref_fas
30.	Figure 15.4.10.1_add	Subjects with Scheduled and Unscheduled Bleeding/Spotting Days by Treatment Cycle – Full Analysis Set	F15_04_10_01_sub_subfsp_cyc_fas
31.	Figure 15.4.10.2_add	Subjects with Scheduled and Unscheduled Bleeding/Spotting Days by Reference Period – Full Analysis Set	F15_04_10_02_sub_subfsp_ref_fas
32.	Figure 15.4.11.1_add	Scheduled and Unscheduled Bleeding/Spotting Days by Cycle – Full Analysis Set	F15_04_11_01_subfsp_day_cyc_fas
33.	Figure 15.4.11.2_add	Scheduled and Unscheduled Bleeding/Spotting Days by Reference Period – Full Analysis Set	F15_04_11_02_subfsp_day_ref_fas
